BIOMEDICAL RESEARCH PROTOCOL
UNIVERSITY OF MISSOURI

Project Title: **A Prospective, Randomized, Non-Blinded, Crossover Controlled Clinical Trial Evaluating the Efficacy of Face Mask Ventilation with 45 Degree Head Rotation in Anesthetized Obese (BMI \geq 35) Adults**

IRB Number: 2012364

Version Number: 1

Version Date: 08/24/2018

Principal Investigator: [name]

Funding Source: Departmental

Clinicaltrials.gov Number: NCT03876873

PI: [name]^{1, 2}
Associate Professor

Co-I: [name], BS²
Medical Student

Co-I: [name], BS, BHS^{1, 2}
Research Specialist

¹Department of Anesthesiology and Perioperative Medicine

²School of Medicine

University of Missouri

Columbia, Missouri 65212

Primary Contact: [name]

Department of Anesthesiology and Perioperative Medicine

University of Missouri–Columbia

[name]

Columbia, MO 65212

[contact]

[contact]

Email: [contact]

2.1 Objectives:

This prospective, randomized, non-blinded, crossover controlled clinical trial will enroll subjects with a BMI ≥ 35 who are undergoing elective surgical procedures. Subjects will be randomized to receive mask ventilation after general induction of anesthesia in either a neutral head position (practice standard position) or a head rotation position (45 degree angle) to determine:

Primary Endpoint:

1. Maximal and average expiratory tidal volume during mask ventilation

Secondary Endpoints:

1. Maximal and average inspiratory tidal volume during mask ventilation
2. Maximal and average end-tidal CO₂ (ETCO₂) during mask ventilation
3. Maximal and average airway flow L/min during mask ventilation
4. Lowest and delta O₂ saturation drop on SpO₂ during mask ventilation
5. Lowest and delta O₂ saturation drop on SpO₂ during intubation

2.2 Clinical Hypotheses:

Primary Hypothesis:

We hypothesize that a 45 degree head rotation during mask ventilation will:

1. Increase the efficacy of mask ventilation measured by tidal volumes

Exploratory Hypotheses:

We hypothesize that a 45 degree head rotation during mask ventilation will:

1. Decrease upper airway obstruction measured by airway flow
2. Improve oxygenation measured by SpO₂ during mask ventilation
3. Improve oxygenation measured by SpO₂ during intubation

3.1 Background & Rationale:

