Mask ventilation is a foundation of airway management after the initial induction of anesthesia. It allows for adequate oxygenation of the patient to buy enough time for intubation, during which the patient is not ventilated. However, in some patients mask ventilation may be difficult – older than 55 years, heavier (BMI > 26 kg/m²), with no teeth, having a beard or sleep apnea.^{1,2,3} Inadequate ventilation, if not corrected, can result in decreasing oxygen saturation to dangerous levels – which could lead to devastating complications. As a result, the efficacy of mask ventilation is of critical importance to patient safety after the induction of anesthesia.

[figure not shown]
A recent study proposed that mask ventilation could be improved simply by turning a patient's head. The study showed that rotating a patient's head to a 45 degree angle significantly improved mask ventilation when compared with the head placed in a neutral position.⁴ However, this study was done in patients with a BMI less than 35. As such, the effects of head rotation on the efficacy of mask ventilation has not been studied in patients with a BMI of 35 and greater.

Obesity (BMI \geq 30 kg/m²) affects almost 40% of US adults and is one of the most prevalent health concerns in our society.⁵ It is a predictor of difficult mask ventilation because it is associated with increased upper airway obstruction, decreased airway patency, and decreased lung volumes such as functional residual capacity (FRC).¹ If previous findings in regard to the effect of 45 degree head rotation on the efficacy of ventilation hold true in the obese patient, then this study will show that head rotation could be used as a simple way to improve the efficacy of mask ventilation for patients with a BMI of 35 and above.⁴

4.1 Study Design:

This will be a prospective, randomized, crossover, non-blinded, controlled clinical trial performed at a single academic hospital.

4.2 Study Design:

4.3 Study Procedures:

I. Subject Population: this study will enroll 38 adults undergoing elective surgery requiring general anesthesia with intubation of the trachea.

II. Inclusion Criteria:

- a. Age \geq 18 years
- b. ASA I-III
- c. BMI \geq 35 kg/m²

III. Exclusion Criteria:

- a. Inability to obtain written informed consent
- b. Pregnant or breastfeeding
- c. Limited head rotation or neck extension
- d. Subjects with expected or history difficult intubation
- e. Large beard
- f. OG/NG tube
- g. GERD

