IV. Randomization: On the day of surgery, before the induction of anesthesia subjects will be randomized into either Group A or Group B. Randomization will be accomplished by the method of randomized permuted block. The two groups will be stratified so that obese subjects with a BMI ≥ 35 and ≤ 44 and those with a BMI ≥ 45 are equally distributed between both groups. Groups will be additionally stratified by the presence or lack of obstructive sleep apnea (OSA).

V. Blinding: Group assignment will not be known by research staff at the time of subject recruitment. No blinding will occur during the clinical portion of the study or during data analysis.

VI. Preoperative Data Collection and Measurements: Before the subject is taken into the operating room, we will record and measure age, BMI, sex, ASA status, preop diagnoses, OSA, procedure being done, Mallampati score, mouth opening, thyromental distance, neck circumference, neck range of motion, lack of teeth, presence of beard, and history of snoring.

VII. Anesthetic Management

a. Monitoring

1. All subjects will be monitored with standard perioperative monitors: ECG, non-invasive blood pressure, pulse oximetry, esophageal temperature, and capnography.

b. Anesthetic Technique

1. All subjects will receive a standardized general anesthetic technique and all anesthetic medications will be dosed on the ideal body weight rather than actual body weight.
2. Preoxygenation – 100% oxygen delivered via face mask for a minimum of 3 minutes

3. Induction – intravenous delivery of propofol, 1.5-2.0 mg/kg, fentanyl, 1 µg/kg, and rocuronium, 0.6 mg/kg. Additional propofol or fentanyl may be administered at the discretion of the anesthesia provider.
4. Mask Ventilation – start when subject loses consciousness. Ventilation settings will be pressure controlled ventilation 20 cmH₂O. Respiratory Rate will be 16. Group A will receive 1 minute of neutral head position followed by 1 minute of 45 degree head rotation to the right and then 1 minute of neutral head position. Group B will be the opposite. If mask ventilation is difficult or SpO₂ saturation drops below 90% the subject will be excluded from the study. Immediately after exclusion the standard of care ventilation will be resumed.
5. Intubation – will be in the standard of care fashion after the 3 sets of head positions are completed. Usually the endotracheal intubation is after 2-3 minutes after induction. Our study may increase that time by 1 or 2 minutes.

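### Randomised subjects are excluded for difficult mask ventilation or SpO₂ below 90%, and no rule keeps their data; read naturally, secondary endpoint 4 cannot show a value below 90%

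*Combined protocol and SAP*

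**What the plan says.** Section 4.3 IV places allocation ahead of the intervention: "before the induction of anesthesia subjects will be randomized into either Group A or Group B". Each subject then has three one-minute periods: neutral, rotated, neutral in Group A and the opposite in Group B. During these minutes section 4.3 VII.b.4 applies: "If mask ventilation is difficult or SpO₂ saturation drops below 90% the subject will be excluded from the study". The next sentence returns the subject to standard-of-care ventilation. 'Difficult' has no definition or threshold. Section 4.3 V adds: "No blinding will occur during the clinical portion of the study or during data analysis".

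Two endpoints in section 2.1 lie close to these triggers. The primary is "Maximal and average expiratory tidal volume during mask ventilation". Secondary endpoint 4 is "Lowest and delta O₂ saturation drop on SpO₂ during mask ventilation", which serves the exploratory hypothesis in section 2.2, "Improve oxygenation measured by SpO₂ during mask ventilation".

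Section 5.1, the only statistical section, is one power sentence. It names no analysis set, no test, and no treatment of values recorded before an exclusion.

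**The concern.** The exclusion comes after randomisation and depends on what happens during the measured minutes. One trigger, SpO₂ below 90%, is itself a value of secondary endpoint 4. If excluded subjects are not analysed, the desaturations that the oxygenation hypothesis is about are the ones removed.

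The other trigger is a judgement made by staff who know the head position. The plan measures the efficacy of ventilation by tidal volume, so a call of 'difficult' may go with low tidal volume, the primary endpoint. That link is an inference, since no section ties the call to a volume.

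The population narrows too. Section 3.1 justifies the trial because "the effects of head rotation on the efficacy of mask ventilation has not been studied in patients with a BMI of 35 and greater", and names obesity as a predictor of difficult mask ventilation. A result limited to subjects who met neither trigger leaves out some of the patients who motivate the question.

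**Working it through.** **Plan's own figure.** Inputs from 5.1: means 450 and 520 ml, SD 75 ml, power 80%, alpha 5% (taken as two-sided). n per group = 2 × (1.960 + 0.842)² × 75² / 70² = 18.02, rounded up to 19. With a two-sample t-test, power at 19 per group is 0.799. The stated 19 reproduces.

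**Endpoint 4.** This needs no assumed rate. If every subject with SpO₂ below 90% is removed, each remaining subject has a lowest value of at least 90%. The drop is baseline minus lowest, so it is at most 100 − 90 = 10 points.

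**Tidal volume, illustration only.** The documents give no exclusion rate and no meaning for 'difficult'. Assumptions: normal tidal volumes with the plan's means and SD; equal correlation rho between a subject's minutes; 'difficult' means tidal volume below a cut-off c; a subject with any such minute is dropped.

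In a single minute, the chance of falling below c is Φ((c − 450)/75) in neutral and Φ((c − 520)/75) in rotation:
- c = 300: Φ(−2.00) = 2.3% against Φ(−2.93) = 0.2%
- c = 350: Φ(−1.33) = 9.1% against Φ(−2.27) = 1.2%

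Low minutes are therefore mostly neutral ones, and dropping those subjects raises the neutral mean more than the rotated mean. Simulating all three minutes (neutral-rotated-neutral in A, rotated-neutral-rotated in B), with stops judged on whole minutes:

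| rho | c (ml) | removed A / B | estimate of the true 70 ml |
|---|---|---|---|
| 0.3 | 300 | 4.5% / 2.5% | 67.4 |
| 0.3 | 350 | 17.0% / 10.8% | 62.4 |
| 0.5 | 300 | 4.3% / 2.5% | 68.2 |
| 0.5 | 350 | 15.8% / 10.3% | 64.6 |
| 0.7 | 300 | 3.8% / 2.4% | 69.0 |
| 0.7 | 350 | 14.2% / 9.7% | 66.8 |

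Stops can also come mid-minute. With 16 breaths per minute (the protocol's rate), an assumed breath-to-breath SD of 40 ml, and a stop when a four-breath running mean falls below c, the estimate is about 58–68 ml, and up to about 30% of Group A is removed.

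Other cases, with whole-minute stops:
- Call unrelated to that minute's tidal volume: 69.9–70.1 ml, so essentially no bias.
- No true effect (450 ml in both positions), same cut-off in both: −0.1 to +0.1 ml.
- No true effect, cut-offs assumed to differ by 50 ml between positions: 2.8–6.5 ml in either direction, type I error about 6–8%.

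**Power.** A paired t-test with exclusions dropped keeps power at 0.997 or more in the whole-minute cases. On the two-group basis of 5.1, power is 0.799 at 19 per group, 0.751 at 17 and 0.694 at 15.

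**Keeping values up to the stop.** A model with position and period that accepts incomplete periods returns 70.0–70.1 ml for the average with whole-minute stops and 70.1–70.5 ml with mid-minute stops. If the call is unrelated to tidal volume, it returns 70.2–71.2 ml. For the maximal tidal volume, a minute cut short has fewer breaths and so a lower maximum, mostly in neutral. The same approach then gives about 71–73 ml against 70, which favours rotation.

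**The case against.** The strongest reply is that exclusion is followed at once by a return to standard-of-care ventilation, so the sentence may describe only a procedural stop with the data kept. That is a possible reading. But no section says the data are kept, and with an unblinded analysis and no defined analysis set the choice could be made after results are seen. A clarifying sentence is needed on either reading.

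A second reply also stands in part. Endpoint 4 is secondary, its hypothesis is exploratory, and every subject receives at least 3 minutes of 100% oxygen first. Values below 90% may be rare, and the documents give no frequency.

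A reader might go further and infer that the primary comparison is selected on its own outcome. The documents do not support that as a fact: 'difficult' is not linked to tidal volume, and every cut-off, correlation and breath SD above is assumed. Nor do they support the opposite inference, that the primary conclusion is safe. That rests on a paired test the plan never names, whereas 5.1 compares two groups.

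A reader might also take endpoint 5 (SpO₂ during intubation) to be cut off at 90%. It is not, because the rule sits in the mask-ventilation step, although excluded subjects would be missing from it on the natural reading.

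**Conclusion.** The concern holds for the data rule. If excluded subjects are not analysed, endpoint 4 is truncated at 90% by the rule itself, whatever the exclusion rate, and the findings apply only to subjects who met neither trigger.

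For tidal volume, bias is a possibility whose size depends on what 'difficult' means in practice. Under the stated assumptions a true 70 ml would shrink to about 62–69 ml (whole-minute stops) or 58–68 ml (mid-minute stops). It would be about zero if the call is unrelated to tidal volume, and could go either way if the call differs by head position. The loss of power is small for a paired analysis. On the plan's two-group basis, power falls from about 80% to about 75% at 17 per group and 69% at 15.

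The clinical stop itself is not in question.

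**What to change.** Leave the clinical stop unchanged and alter only the data rule.

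- **Section 4.3 VII.b.4:** state that study positioning stops, but the subject stays in the study and in the analysis.
- **Section 5.1, analysis set:** all randomised subjects in whom mask ventilation began are analysed by head position, using recorded values up to and including the stop, with a method that accepts incomplete periods. A linear mixed model with position and period as fixed effects and subject as a random effect is one option.
- **Endpoint 4:** include the SpO₂ value at the stop, and state that any deeper fall afterwards is censored.
- **Maximal tidal volume:** set a partial-minute rule. For example, treat the average as the main measure for stopped minutes, and give the maximum with and without them.
- **Reporting:** give the number of stops and their reasons by head position.

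The cost is one sentence in 4.3, a few in 5.1 and one reason-for-stop field. The team must also confirm that values up to the stop are captured. Some subjects will contribute incomplete minutes, and one stopped in the first minute gives no within-subject contrast. SpO₂ stays censored at the stop, so the truncation is reduced and not removed. A small bias in the average may remain, within about 1 ml in the checks above.

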6. The study will conclude with intubation of the trachea. The rest of the subject management will be per anesthesia clinical team standard of care.

c. Extubation

1. Standard of care.

VIII. Postoperative Pain Management

a. Standard of care.

4.4 Costs:

The cost of the Medline Top Valve Anesthesia Mask used in this study will be billed to subjects' insurance as normal standard of care at University Hospital. Face masks are used on surgical patients as standard of care following University Hospital Department of Anesthesiology and Perioperative Medicine protocol. They are necessary for

preoxygenation of patients before surgical procedures. Taking part in this study will bring no additional cost to subjects.

4.5 Study Duration:

Study will start in September 2018 and last one year.

5.1 Statistical Analysis and Sample Size Justification:

A power analysis using a predicted tidal volume of 450 ml for group A and 520 ml for group B, with a standard deviation of 75 ml, determined that 19 subjects per group would be needed to achieve a power of 80% with an alpha error of 5%.

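### The 80% power in section 5.1 is for two independent groups, but groups A and B are crossover sequences and no within-subject analysis is named

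*Combined protocol and SAP*

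**What the plan says.** Section 4.1 describes the design: "This will be a prospective, randomized, crossover, non-blinded, controlled clinical trial performed at a single academic hospital". Section 4.3 VII.b.4 defines the groups by order of head position. "Group A will receive 1 minute of neutral head position followed by 1 minute of 45 degree head rotation to the right", and then returns to neutral for a third minute; "Group B will be the opposite", which I read as rotated, neutral, rotated. The primary hypothesis in section 2.2 is that rotation will "Increase the efficacy of mask ventilation measured by tidal volumes". The primary endpoint in section 2.1 is "Maximal and average expiratory tidal volume during mask ventilation".

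Section 4.3 I gives the total: "this study will enroll 38 adults undergoing elective surgery". Section 5.1 consists of one sentence. Its inputs are "a predicted tidal volume of 450 ml for group A and 520 ml for group B, with a standard deviation of 75 ml", and its result is that "19 subjects per group would be needed to achieve a power of 80% with an alpha error of 5" (per cent). It names no test or model and gives no within-subject correlation. It does not say whether 75 ml is the SD of one measurement or of a within-subject difference, or which of the two tidal-volume measures the figures refer to.

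**The concern.** The two predicted means are assigned to groups, yet each group spends time in both positions. A 70 ml effect of rotation is a difference between positions, not between A and B. A calculation for independent groups therefore answers a question that the crossover does not ask, and the 80% is not the power of the comparison that the hypothesis calls for.

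Two things are at stake. A reader cannot tell from section 5.1 what size of position effect 38 subjects can detect. And because this sentence is the only statistical text in the protocol, the primary analysis is left open: how the two positions are compared, how the repeated position is used, and which tidal-volume measure decides the result.

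**Working it through.** **Inputs from the documents.** Means 450 and 520 ml (difference 70 ml), SD 75 ml, 19 per group, power 80%, alpha 5% (section 5.1); 38 subjects and three one-minute periods (section 4.3).

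**Assumptions.** The test is two-sided (not stated, but a one-sided test would need 15 per group and does not match). The within-subject correlation rho is not given, so a range is shown, with equal correlation between all minutes. All 38 subjects complete.

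**Step 1: the plan's own figure.** For two independent means, n per group = 2 × (1.960 + 0.842)² × 75² / 70² = 18.02, rounded up to 19. The t-test power at 19 per group is 79.9%. The stated figure is reproduced.

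**Step 2: the within-subject comparison, if 75 ml is the SD of a single-position measurement.** Two versions bracket the result.

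- *Two-value paired:* one value per position per subject. SD of the difference = 75 × √(2(1 − rho)), 37 df.
- *Three-period contrast:* minute 2 minus the mean of minutes 1 and 3, compared between sequences and halved. SD = 75 × √(1.5(1 − rho)), 36 df.

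In both, the standard error is SD/√38. At rho 0 it is 106.1/√38 = 17.2 ml (paired) or 91.9/√38 = 14.9 ml (three-period). A two-sided 5% test with 80% power needs an effect of about 2.88 standard errors.

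| rho (assumed) | Power for 70 ml: paired / three-period | Smallest effect at 80% power: paired / three-period |
|---|---|---|
| 0 | 97.7% / 99.5% | 49.5 / 42.9 ml |
| 0.5 | >99.9% / >99.9% | 35.0 / 30.3 ml |
| 0.8 | >99.9% / >99.9% | 22.1 / 19.2 ml |

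At rho 0, 80% power for 70 ml would need 21 subjects in total (paired) or 16 (three-period, equal split).

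**Step 3: if 75 ml is the SD of within-subject differences.** Standard error = 75/√38 = 12.2 ml. Power for 70 ml exceeds 99.9%, and the smallest effect at 80% power is 35.0 ml.

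**Step 4: could the 80% belong to some other comparison of A with B?**

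- *All three minutes.* A has one rotated minute of three and B has two, so the expected difference is 70/3 = 23 ml. The SD of a three-minute mean is 75 × √((1 + 2 rho)/3), which gives power of 37% at rho 0 and 16% at rho 0.9. This does not fit.
- *First minute only.* A is neutral and B rotated, so the expected difference is 70 ml with SD 75 ml and 19 per group. Power is 79.9%. This fits, but no section plans it.

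**Step 5: carryover.** Positions change every minute and no washout is described. Let t be the position effect and c the extra carryover from a rotated minute into the next. In A the contrast in step 2 has mean t − c/2; in B it has mean −t + c. Half the difference is t − 0.75c. With an assumed c of 20 ml, a true 70 ml would be estimated as 70 − 15 = 55 ml. The first-minute comparison is free of this.

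**The case against.** The strongest reply is that section 5.1 may be right as written for a first-minute comparison. Section 2.1 speaks of randomizing subjects to one position or the other, and in minute 1 group A is neutral and group B rotated. The means, the SD, the 19 per group and the 80% all fit, and that comparison is free of carryover. The numerical fit stands. But no section plans a first-minute analysis, the trial is declared a crossover, and using only that minute would discard the within-subject information.

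A second reply is that using the parallel-group formula for a crossover is a defensible, cautious choice when no correlation is known. That also stands as far as N is concerned. Section 5.1 does not say that this was the reasoning, and the 80% still does not describe the crossover comparison.

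A reader might infer that an unpaired analysis is intended. The documents do not show this: a sample-size formula is not an analysis plan, and section 5.1 names no analysis at all. A reader might also infer an arithmetic slip or a shortage of subjects. Neither is supported: the arithmetic is correct for its formula, and the mismatch leaves more power than stated. Finally, nothing in the protocol says that effects below 70 ml are of interest, so the smaller detectable effects describe the design and are not a target that the trial has missed.

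**Conclusion.** The concern holds as a mismatch between the calculation and the design, together with an unnamed primary analysis. The stated 80% is not the power of the rotated-versus-neutral comparison in 38 subjects. That power is at least 97.7% for 70 ml at any non-negative correlation if 75 ml is a single-position SD, and above 99.9% if it is the SD of differences. The direction is conservative, and N = 38 need not change.

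The exact detectable effect rests on the assumed correlation, on the unstated meaning of the SD and on all subjects completing. The conclusion that 80% is the wrong figure holds under both meanings of the SD. It would weaken only with negative correlation or heavy exclusions after randomization. This should be fixed, but it does not threaten the trial's ability to detect the difference it assumes.

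**What to change.** Keep N = 38 and rewrite section 5.1 as follows.

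- Attach 450 ml to the neutral position and 520 ml to the rotated position, and say what the 75 ml SD describes.
- Say which of maximal or average expiratory tidal volume is primary, and that this is the one powered.
- Name a within-subject primary analysis: a mixed model with position, period (minute 1, 2 or 3) and sequence as fixed effects and a random subject effect, reporting rotated minus neutral with a 95% CI. With complete data, the halved between-sequence contrast in step 2 gives the same point estimate but not the same degrees of freedom, so one of the two should be fixed in advance.
- State that the analysis assumes no carryover between consecutive minutes. Give the first-minute comparison of A with B as a carryover-free sensitivity analysis, with about 80% power for 70 ml at 19 per group if 75 ml is the single-position SD.
- Restate power as the smallest position effect detectable with 38 subjects over a stated range of within-subject correlation.

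The cost is a reworded section, with no extra subjects or measurements. The drawback is that the restated power rests on an assumed correlation range, because the protocol gives no within-subject variance.
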